serological criteria, will be recruited for this study. 42 will undergo oral immunotherapy, while 42 will be followed as natural history controls but will be offered similar therapy, should it be successful, at the completion of one year. OIT subjects will initiate therapy with a 2-day rush desensitization treatment using oral doses of milk, in our Clinical Investigation Unit. They will then continue the highest tolerated dose of milk at home for two weeks. Subsequently, they will return for weekly increases in doses until a maximum of 200 ml of milk is ingested daily. The primary clinical outcome will be a comparison of the amount of milk consumed safely on oral challenge performed prior to OIT, when the OIT dose has reached its maximum (200 ml or highest tolerated dose) and after one year of therapy. Patients will also be followed with clinical symptom scores and adverse event diaries and we will monitor immunological parameters such as changes in milk-specific IgE, blocking antibodies (IgG4 and IgA) and regulatory T and B cells. We expect that we will be able to see important improvement in the ability to safely ingest milk and other dairy products, and this will be accompanied by significant decreases in IgE and increases in Regulatory T and B cells.

BACKGROUND INFORMATION:

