Through a process of stratified randomization (according to sex), participants will be randomly assigned to one of 2 study groups. The first group will receive active desensitization, and the second group will not receive any treatment but will be followed up regularly (Appendix A Table 2). Desensitization will be offered to the observation groups following the trial, should the outcome be successful in the treatment group.

3.2 Oral challenge test to milk. Prior to initiating desensitization and following treatment, the subjects will undergo a placebo controlled oral challenge to milk. These challenges will determine the level at which the children react and will be the baseline to follow their improvement in oral tolerance following therapy.

Oral challenges will be single blinded and will be performed with fresh cow's milk, with increasing doses taken orally every 10 to 15 minutes up to a total of 150ml of milk (doses of 0.1, 0.3, 1.0, 3.0, 10.0, 30.0, 45ml, 60 mL) ^{(49,82) (83)}. Patients will receive 2 challenges per day, 1 placebo and 1 with the active substance (milk). Nurses in the Medical Day Unit/Center for Investigative Medicine will prepare the food and randomize the placebo challenges. Unless contraindicated, the placebo will be soy or rice-based milk. If the challenge is negative after 150 ml of milk, results will be confirmed by means of open challenge, using 250ml of yogurt or ice cream 1 hour after completion of the blinded portion(29) according to the recommendations of the European Academy of Allergology and Clinical Immunology (5). After completing the challenge, patients will be kept under observation for at least 2 hours. Only objective symptoms will be considered to be indicative of a positive allergic reaction (29). Food challenges will be scored as positive if a single symptom or any of the following objective clinical reactions will be observed: urticaria, angioedema, wheezing, rhinitis, vomiting, diarrhea, protracted abdominal pain, exacerbation of atopic dermatitis, or shock. A single episode of vomiting will not be considered as a positive reaction, while severe and repetitive vomiting will. If the challenge is **negative**, ie, the subject is asymptomatic, he/she will be excluded from the study. Based on our experience, approximately 80% of those subjects ages 6 or greater, with positive history and positive skin tests, approached will fail the oral challenge and thus be eligible.

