3.3.3 Maintenance phase

Patients who reach the maintenance dose of 200 ml will be instructed to continue and consume 200 ml of milk daily for 1 month. They will then undergo an oral challenge (see above), with the maximum dose of 300ml.

If this 300 ml dose is tolerated, they will be permitted to consume dairy products without restrictions and attend regular follow up visits for 12 months. It will be recommended to consume dairy at least twice weekly, if not more, to maintain the desensitization.

Subjects who tolerate less than the 200 ml upper dose will be instructed to continue their maximum tolerated dose for the 12 month follow-up period, at which time another blinded milk challenge will be performed to determine if their tolerance increased.

3.3.4 Long Term Follow-up: to assess the persistence of milk desensitization from clinical, cellular and molecular perspectives, participants will be asked to return to the research center once a year for five years following the end of the Maintenance Phase. At these visits, participants will be asked about their dairy consumption, any reactions they may have experienced in the interval between the last visit and changes in their quality of life (as assessed by questionnaire). Participants will also have the following analyses done: SPT, salivary IgA, serum milk-specific IgE, IgA and IgG4 concentrations, Glycosylation state, Vitamin D levels, and B and T cell regulatory cell phenotyping. Participants will be reminded of the importance of continuing the consumption of dairy products in the maintenance of desensitization. Participants who have completed the study will be asked to reconsent to the extension. Given that these participants may not have scheduled visits to the hospital, to lessen their inconvenience, a delegated member of the study team might make a home visit in order to obtain informed consent

3.3.4 Control Subjects: Subjects randomized to no treatment will be followed every 3-6 months as is standard in our clinic for milk allergy. They will have skin testing and blood testing as on routine follow-ups, but they will be required to fill out symptoms diaries. At the end of the study period, oral desensitization will be offered to the control patients who had not spontaneously achieved tolerance.

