Withdrawal from therapy: Subjects will be carefully monitored during the in hospital rush therapy phase, as well as during the home OIT phase. Instructions for treatment of reactions will be provided as above. Patients who are enrolled will be informed that in previously published studies, minor allergic reactions are common in these protocols (mild itching, abdominal discomfort) but resolve with increased time on therapy. Subjects will be withdrawn if they cannot tolerate the low dose, rush desensitization phase, if they have more than 2 or more moderate or severe reactions during the home (maintenance) OIT phase, if they experience a rare or unforeseen complication such as severe flares of eczema or chronic gastrointestinal symptoms (e.g. development of eosinophilic esophagitis) and if the parents or subjects wish to voluntarily terminate therapy.

3.3.6 : Variables measured. The following variables will be measured in each patient:

A. The primary outcome measure will be the presence of desensitization defined by the ability to tolerate 200 ml of milk 1 year after the start of the trial. This is a qualitative variable with three categories: total desensitization (200 mL of cow's milk); partial desensitization (20–200 mL); and failed desensitization (<20 mL milk). Only patients presenting total desensitization were regarded as being successfully desensitized.

B. Secondary outcome measures will be:

1. Number and severity of adverse reactions occurring after oral exposure to milk during the desensitization and follow-up phases.
2. Minimum dose of milk that triggered symptoms during the desensitization protocols or challenge tests.
3. Days until desensitization was achieved.
4. Indices of desensitization :
 - a. Change in skin prick test weal size, comparing tape transferred, cpoputor measured diameters and areas of the skin tests to milk extract.
 - b. Levels of sIgE, sIgA and sIgG4 before desensitization, during follow-up and at the end of the study.
 - c. T and B reg before desensitization, during follow-up and at the end of the study.

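### The milk challenges as written cannot score the primary outcome (200 mL of milk tolerated at 1 year) on one scale and one date in every patient

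*Combined protocol and SAP*

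**What the plan says.** **Outcome.** Section 3.3.6 opens with "The following variables will be measured in each patient" and defines the primary outcome as "the ability to tolerate 200 ml of milk 1 year after the start of the trial". It has three categories: total (200 mL), partial (20 to 200 mL) and failed (under 20 mL). Only total is success. The Experimental Approach names oral challenge as the instrument, before OIT, "when the OIT dose has reached its maximum (200 ml or highest tolerated dose) and after one year of therapy".

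**Challenge procedure.** Section 3.2 states: "Prior to initiating desensitization and following treatment, the subjects will undergo a placebo controlled oral challenge to milk". Fresh milk is given in "increasing doses taken orally every 10 to 15 minutes up to a total of 150ml of milk", listed as "doses of 0.1, 0.3, 1.0, 3.0, 10.0, 30.0, 45ml, 60 mL". A negative result is followed an hour later by an open step of 250 mL of yogurt or ice cream.

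**Treated patients.** Under Section 3.3.3, those who reach 200 mL stay on it for a month and then have a challenge whose maximum is raised to 300 mL. If they pass, they may eat dairy freely, with intake at least twice a week advised, and attend visits for 12 months. Those below 200 mL keep their highest dose for a 12-month follow-up, "at which time another blinded milk challenge will be performed to determine if their tolerance increased". Nothing further is stated for a patient who reaches 200 mL but reacts in the 300 mL challenge.

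**Controls.** They "will be offered similar therapy, should it be successful, at the completion of one year". The Control Subjects paragraph lists skin tests, blood tests and diaries. Section 5 makes a positive challenge after the observation year a condition for receiving OIT. The randomisation paragraph cites Appendix A Table 2 for follow-up, and that table is not in the available text.

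**Visit schedule.** Appendix C has a baseline challenge at Visit 2 and one later challenge at Visit 24, a month after OIT stops. Neither Visit 23 (a month after escalation) nor Visit 28 (12 months after OIT completion) lists one.

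**The concern.** An outcome with a stated volume and date needs a test that reaches that volume, on that date, in everyone who is compared. If sites work from Section 3.3.3 and Appendix C, the three categories would instead come from challenges with different ceilings and dates. Treated patients who do well would be tested to 300 mL months before the endpoint. Those who do less well would be tested later, with no stated maximum. Controls would be tested on a ladder whose milk steps stop short of success.

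The between-arm comparison of the one success category would then mix the treatment effect with differences in measurement. A control who outgrew the allergy could finish every milk step and still have no rule placing them in the total category. An early pass also does not settle the one-year state: Section 1.13 itself describes desensitization as temporary and dependent on regular exposure.

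**Working it through.** **1. Ladder.** Inputs: the eight doses in Section 3.2 and the cut-offs in Section 3.3.6. Section 3.3.6 does not say whether 200 mL is a single portion or a running total, so both readings are shown.

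| Dose (mL) | Running total (mL) | Category by single dose | Category by running total |
|---|---|---|---|
| 0.1 | 0.1 | failed | failed |
| 0.3 | 0.4 | failed | failed |
| 1 | 1.4 | failed | failed |
| 3 | 4.4 | failed | failed |
| 10 | 14.4 | failed | failed |
| 30 | 44.4 | partial | partial |
| 45 | 89.4 | partial | partial |
| 60 | 149.4 | partial | partial |

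The sum, 149.4 mL, reproduces the plan's 150 mL after rounding. The shortfall from 200 mL is 200 − 149.4 = 50.6 mL on the running total and 200 − 60 = 140 mL on the single dose. Neither reading reaches total. The gap to the Section 3.3.3 maximum is 300 − 149.4 = 150.6 mL.

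Counting the open step would give 149.4 + 250 = 399.4 mL of dairy. But that step is unblinded, is not milk, and is nowhere linked to the 20 and 200 mL cut-offs.

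**2. Dates.** Inputs: Appendix B reaches 200 mL at week 17 and runs to week 52. Section 3.3.3 adds one month, taken as 4.35 weeks. Assumption: the undefined start of the trial is the start of Appendix B dosing, so the endpoint falls at week 52.

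| Group | Source | Milk maximum | Week | Against week 52 |
|---|---|---|---|---|
| OIT, reached 200 mL | 3.3.3 | 300 mL | 17 + 4.35 = 21.35 | 52 − 21.35 = 30.65 weeks early |
| OIT, below 200 mL: 12 months end with the last Appendix B row | 3.3.3 | not stated; default 150 mL | 52 | on time |
| OIT, below 200 mL: 12 months run from end of escalation | 3.3.3 | not stated; default 150 mL | 17 + 52 = 69 | 69 − 52 = 17 weeks late |
| OIT, Visit 24: stopping means the end of the Appendix B row | Appendix C | not stated; default 150 mL | 52 + 4.35 = 56.35 | 4.35 weeks late |
| Controls | implied by Section 5 | default 150 mL | after one year; no visit listed | not fixed |

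No row combines a milk maximum of at least 200 mL with a one-year date. Visit 24 is also tied by Section 1.13 to another question, lasting tolerance after stopping.

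**3. Could daily dosing stand in?** Appendix B shows 200 mL daily in weeks 17 to 52. Section 3.3.3 releases those who pass to free dairy at about week 21, with only twice-weekly intake advised. Controls have no counterpart at all.

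**The case against.** The strongest reply is that the protocol must be read as a whole. The Experimental Approach foresees a challenge after one year of therapy, Section 3.3.6 fixes one year in each patient, and Section 5 implies a one-year challenge for controls. This stands against anyone who infers that the plan contains no one-year challenge. What remains is that Section 3.3.3 and Appendix C do not carry it through for patients who reach 200 mL, and no text gives it a maximum that reaches the success threshold.

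A reader might also infer that controls have no challenge dose. That is too strong. Section 3.2 is the general procedure, so the 150 mL ladder applies to them by default. The trouble is that it stops too low. Appendix A Table 2 may say more about controls, but it is cited only for their follow-up and would not obviously mend the treated arm's schedule.

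Third, Section 3.3.3 expressly raises the ceiling to 300 mL after OIT, and on a running-total reading anyone who reacts before 149.4 mL is already short of total. Both points are right. They confine the ladder problem to people who finish 149.4 mL outside the 300 mL challenge; they do not remove it.

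Fourth, the week counts depend on a clock that the plan does not define. This also stands. Placing Visit 24 at week 21, by reading the stop of OIT as the end of escalation, is unlikely because it would coincide with Visit 23.

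**Conclusion.** The concern holds, and it needs an amendment: the stated procedures cannot score the stated primary outcome on one scale and date. That the default milk ladder falls 50.6 mL short (running total) or 140 mL short (single dose) is firm. So is the absence of a stated one-year challenge for patients who reach 200 mL, both in Section 3.3.3 and at Visit 28.

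The timing gaps are conditional. The 300 mL challenge comes about 31 weeks early, and the challenge for patients below 200 mL is on time or about 17 weeks late. Both figures assume that trial start equals the first week of Appendix B, and the second also depends on where the 12 months begin.

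A reader might infer that the mismatch favours OIT, or favours controls. The documents give no basis for either. They do not show how many participants would finish 149.4 mL, or how many would lose tolerance after month 5, so the size and direction of any bias are unknown.

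**What to change.** Amend Sections 3.2 and 3.3.3, the Control Subjects paragraph and Appendix C as follows.

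- **Date and population.** Hold the one-year challenge already foreseen in the Experimental Approach and Section 5 at 12 months from randomisation, in every randomised participant who can be challenged, before any control crosses over.
- **Ladder.** Use the same blinded milk ladder in both arms, extended to the 300 mL maximum of Section 3.3.3. For example, add steps of 60 and 90 mL: 149.4 + 60 = 209.4 mL, then 209.4 + 90 = 299.4 mL.
- **Cut-offs.** State whether 20 and 200 mL are running totals or single portions. If single portions, adding a 200 mL step gives 149.4 + 200 = 349.4 mL, above the 300 mL maximum. Either re-space the ladder so that a 200 mL step fits, or state the higher total. Assign exactly 200 mL to total only, because it now falls in both total and partial.
- **Scoring.** State that the yogurt or ice cream step does not count toward the cut-offs, and take the primary outcome only from this challenge.
- **Other challenges.** Keep the 300 mL challenge at about month 5 as the gate to unrestricted dairy and list it at Visit 23. Define the stopping point that Visit 24 counts from.

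The cost is a protocol amendment, an aligned visit table and one 12-month challenge with its reaction risk. For patients who responded, that challenge is already foreseen in the Experimental Approach; for controls who would not seek OIT it is an addition. The two extra steps add 2 × 10 = 20 to 2 × 15 = 30 minutes, only for those who tolerate 149.4 mL.

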3.3.2 Escalation phase

Once subjects reached the dose of 2.5 ml undiluted milk, they will be instructed to repeat this dose at home daily for 2 weeks. They will then come to the research unit, and will be given an increased dose of 4 ml. This will be continued for one week, with incremental increases given weekly for 16 weeks, until a dose of 200 ml is reached. If a patient is unable to increase past a particular dose they will continue on this dose until the end of the 16 week acceleration phase.

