3.3.4 Documentation: Subjects and families will be asked to complete daily home diaries to document that daily doses were taken, as well as to report accidental ingestions, problems with dose administration, or related symptoms. Follow-up visits in addition to or in conjunction with the weekly visits for dose escalation will be at 3, 6, 9, 12 months from completion of OIT. Each visit will include a medical history and physical examination, SPT, serum milk-specific IgE, IgA and IgG4 concentrations, Vitamin D levels, and B and T cell regulatory cell phenotyping will be measured at enrollment and at follow-up visits. (see Appendix C). Biweekly or monthly Telephone follow-up of these patients will be done prior to and following reaching the maximum tolerated dose. The telephone follow-up will review symptoms

and protocols for how to treat potential reactions.

3.3.5 Adverse reactions to OIT: All patients and their caregivers (if applicable) will be provided self-administered epinephrine, along with instructions and indications for administration and education about the nature of possible reactions to the desensitization therapy. Home diary forms will be provided to record the dose, date and time taken, symptoms occurring after the dose or any other time, and medications taken each day (Appendix D).

Safety measures: The patients' caregivers will be instructed **verbally and in writing** about the recommendations to be followed after desensitization and how to **treat** possible allergic reactions. They will also be given telephone and pager numbers of investigators and nurses for direct consultation 24/7. Parents will be instructed to contact the research team should any symptoms suggestive of an allergic reaction be present (appendix E, bottom of page).:

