4.0. Statistical Considerations

A: Sample Size calculation: Given that previous studies have attributed at least 50% improvement in the ability to tolerate milk(24) with an α of 0.05 and a power (1- β) of 0.80, a sample of 42 cases and 42 controls will be recruited.

B: Statistical Analysis: Statistical analyses will be performed using paired t-tests. A p value of <0.05 will be considered significant. Descriptive statistics of the variables including means, standard deviations and frequencies were computed for all study variables. The concentrations of milk –specific IgE, IgG and IgA, the size of the skin tests , T reg and Breg expression at the different study time-points will be compared with their baseline values using the one-sample paired t-test and to the control using a 2 sample t-test .

Multiple regression models will be used to assess factors associated with response to desensitization, including baseline demographic characteristics; gender; age; baseline SPT and specific IgE, Treg and Breg numbers, and vitamin D level.

5. Ethical Considerations

In the consent form given at study enrolment, participants will be advised that they will be randomly assigned to either oral immunotherapy or observation for a one year period. Participants will also be advised that their data will be shared only among the OIT study team. Participants in the observation control group who will not receive OIT treatment, will be told that they may to undergo such therapy after a year of observation and a positive oral food challenge.

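### The OIT and control arms' marker visits run on different clocks, and no rule matches dates or drops control data once controls may have started OIT

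*Combined protocol and SAP*

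**What the plan says.** **OIT arm.** Under the Documentation heading (one of three sections numbered 3.3.4), follow-up visits with skin tests, antibodies and regulatory-cell phenotyping "will be at 3, 6, 9, 12 months from completion of OIT". Appendix C adds draws one week (Visit 22) and one month (Visit 23) after the escalation visits. It then counts Visits 24 and 25 from cessation of OIT and Visits 26 to 28 from completion of OIT. Only Visit 23 ties completion explicitly to escalation. Appendix B runs the full dose from week 17 to week 52.

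**Control arm.** Under Control Subjects: "Subjects randomized to no treatment will be followed every 3-6 months as is standard in our clinic for milk allergy". The next sentence adds: "They will have skin testing and blood testing as on routine follow-ups". No anchor date is given, and regulatory-cell draws are not mentioned there.

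**Analysis.** Section 4.0 B compares antibodies, skin tests, Treg and Breg at the study visits with baseline by paired t-test "and to the control using a 2 sample t-test". It has no visit windows, no pairing of visits across arms and no rule for control data after OIT begins.

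**When controls may start OIT.** Four places bear on this:
- Experimental Approach: controls "will be offered similar therapy, should it be successful, at the completion of one year".
- Section 5: after one year of observation and a positive challenge.
- Section 3.1 (randomization paragraph): after the trial, if treatment succeeds.
- Control Subjects: at the end of the study period, undated.

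**The concern.** A two-sample test of a marker estimates a treatment effect only if both arms are measured at comparable times and the comparator is untreated. Neither is secured here.

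The plan gives its own reasons to care about elapsed time. Section 1.5 describes milk allergy resolving with age. The Control Subjects paragraph allows for controls who become tolerant spontaneously. Section 1.11 names vitamin D fluctuation in a northern climate as a possible confounder. If the arms are sampled at different elapsed times or in different seasons, those influences enter the difference between arms. The OIT anchor may also depend on response, because Appendix C allows extra escalation visits, so slower escalators could be sampled later.

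The second problem is the comparator. Section 1.10 intends a comparison with untreated children, but two sections assure that status for one year only, and some marker visits fall later than that. What is at stake is the between-arm evidence for objectives 3 (blocking antibodies) and 4 (Treg and Breg).

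**Working it through.** The plan gives no figure on this point to reproduce. The check is calendar arithmetic.

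**Inputs**
- First home dose: "they will be instructed to repeat this dose at home daily for 2 weeks" (Section 3.3.2).
- Escalation: "with incremental increases given weekly for 16 weeks, until a dose of 200 ml is reached" (Section 3.3.2).
- Full dose first listed at week 17; table ends at week 52 (Appendix B).
- Visits 3, 6, 9 and 12 months after completion (Documentation; Appendix C).
- Earliest control OIT: month 12 (Experimental Approach; Section 5).
- Assumption: OIT starts at randomization. One month = 365.25 / 12 / 7 = 4.348 weeks.

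**Step 1. Date of completion under each reading**
- Appendix B, week 17: 17 / 4.348 = 3.9 months.
- Section 3.3.2, 2 + 16 = 18 weeks: 18 / 4.348 = 4.1 months.
- End of Appendix B, week 52: 52 / 4.348 = 12.0 months.

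**Step 2. Visit dates (completion month + 3, 6, 9, 12)**

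| Completion | 3 mo | 6 mo | 9 mo | 12 mo | After month 12 |
|---|---|---|---|---|---|
| Week 17 | 6.9 | 9.9 | 12.9 | 15.9 | 2 of 4 |
| Week 18 | 7.1 | 10.1 | 13.1 | 16.1 | 2 of 4 |
| Week 52 | 15.0 | 18.0 | 21.0 | 24.0 | 4 of 4 |

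**Step 3. Early draws.** Counted from the end of escalation, Visit 22 falls at (17 + 1) / 4.348 = 4.1 to (18 + 1) / 4.348 = 4.4 months, and Visit 23 at 3.9 + 1 = 4.9 to 4.1 + 1 = 5.1 months. Both precede any crossover. Neither has a matching control date.

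**Step 4. Sensitivity to a lag.** If OIT starts 1 to 2 months after randomization (assumption), the week-17 visits move to 7.9–8.9, 10.9–11.9, 13.9–14.9 and 16.9–17.9 months: still two of four after month 12. With week 18 and a full 2-month lag, the 6-month visit reaches 10.1 + 2 = 12.1, which makes three of four.

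**Step 5. Size of the date mismatch.** With control visits up to 6 months apart, an OIT visit can be at most 6 / 2 = 3 months from the nearest one. If control visits were evenly spaced from the start (assumption), the worst miss for the 6.9-month visit is 2.3 months (visits every 4.6 months, at 4.6 and 9.2). For the 9.9-month visit it is 12 − 9.9 = 2.1 months (visits every 6 months).

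**Step 6. Dilution, as an illustration only.** The plan gives no marker SD or effect. Assume a standardized difference of 0.611, which gives 80% power at 42 per arm (two-sided 0.05), and assume crossed-over controls show the full OIT effect. With share c crossed over, power = Φ(0.611 × (1 − c) × √(42/2) − 1.96):
- c = 0: Φ(2.80 − 1.96) = 80%
- c = 25%: Φ(2.10 − 1.96) = 56%
- c = 50%: Φ(1.40 − 1.96) = 29%
- c = 75%: Φ(0.70 − 1.96) = 10%

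The full-effect assumption is an extreme. On the week-17 clock, a control starting at month 12 has had 12.9 − 12 = 0.9 months of OIT at the third visit and 15.9 − 12 = 3.9 months at the fourth.

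**The case against.** The strongest reply is that controls may never cross over during the marker visits. Section 3.1 and the Control Subjects paragraph place the offer after the trial or at the end of the study period, and every version carries a condition: success in the treated arm, a positive challenge, or no spontaneous tolerance. This stands in part. A reader might infer that the later tests have definitely lost their untreated comparator. The documents do not establish that, because they contradict each other on the date. But if controls do wait, the mismatch of clocks remains.

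A reader might also infer that control visits are timed from enrolment. No section says so; the anchor is simply absent. Section 3.1 cites a Table 2 in Appendix A that is not in the available text and may hold a control schedule, so its absence is not counted against the plan.

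Third, objectives 3 and 4 ask whether successful OIT goes with increases in the markers, and the paired tests against baseline address that within the OIT arm. This stands: to say that the objectives as a whole are undermined would go too far.

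Finally, crossed-over controls who respond to OIT would shrink a true difference rather than create a false one, and no marker drift or seasonal effect is quantified. Both points are fair. They limit the size that can be claimed, but do not justify testing arms at unmatched times.

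**Conclusion.** The concern holds for the between-arm marker comparisons only. As written, Section 4.0 B would compare arms at different elapsed times and, after month 12, possibly against controls already on OIT. Two of the four post-completion visits are exposed if completion is week 17 or 18, and four of four if it is week 52. The draws at about months 4 to 5 come before any crossover but are also unmatched.

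The counts assume that OIT starts at or soon after randomization and that controls may start at one year, as the Experimental Approach and Section 5 allow. The bias from unmatched dates cannot be sized from the documents, and the power figures are illustrative.

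The within-arm paired tests are not affected. Nor is the primary outcome, which Section 3.3.6 sets at one year from the start of the trial. The plan should be changed, but the main efficacy conclusion does not depend on it.

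**What to change.** 1. Define completion of OIT once, and use it consistently in the Documentation section and Appendix C.
2. Reconcile the Experimental Approach and Section 5 with Section 3.1 and Control Subjects on when controls may start OIT.
3. Time marker draws in both arms from randomization.
4. Make the main between-arm marker comparison at month 12, drawn before any control starts OIT and adjusted for the baseline marker value already collected. Treat month 6 as supportive.
5. Exclude control data after OIT starts from between-arm tests, and describe later OIT-arm data within the arm only. Controls still untreated after a year would be a selected group, since those with a positive challenge can leave for OIT and those who became tolerant stay.

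**Cost.** More than a change of SAP wording, but small. On the week-17 clock, the OIT draws at about 6.9 and 12.9 months each move about 0.9 months earlier. Control visit dates must be fixed, and the sponsor must confirm that controls have Treg and Breg drawn then, because the control paragraph promises only routine testing. If completion proves to mean week 52, the month-12 OIT draw may have to be added rather than moved.
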